# Précis

To test the hypothesis that the regimen of flutamide (an antiandrogen), testolactone or letrozole (an inhibitor of androgen-to-estrogen conversion), and reduced hydrocortisone dose can normalize the growth and adult stature of children with congenital adrenal hyperplasia, and can avoid the complications of supraphysiologic glucocorticoid dosage, 60 children with this disorder will be randomized to receive either the above regimen or conventional treatment until they have reached age 13 years in a girl or age 14 in a boy. After these ages boys will receive conventional treatment and girls will receive conventional treatment plus flutamide. In girls, flutamide will be continued until 6 months after menarche. All children will be followed until they have attained final adult height. The principal outcome measures will be adult height, body mass index, and bone density.

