### Secondary Objectives

- To assess the safety and tolerability of antiandrogen, aromatase inhibitor and reduced hydrocortisone dose combination therapy.
- To assess the effect of antiandrogen, aromatase inhibitor and reduced hydrocortisone dose combination therapy on height gain, growth velocity and bone maturation prior to puberty.
- To assess the effect of antiandrogen, aromatase inhibitor and reduced hydrocortisone dose combination therapy on height gain and bone maturation during puberty
- To assess the effect of antiandrogen, aromatase inhibitor and reduced hydrocortisone dose combination therapy on development of TART in males and establishment of menstrual regularity in females
- To assess the effect of antiandrogen, aromatase inhibitor and reduced hydrocortisone dose combination therapy on fasting glucose, body mass index, and bone mineral density
- To assess hormonal control based on percent of visits within the normal (or optimal) range for 17OHP, androstenedione, PRA and ACTH
- To assess sex differences in outcomes.

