Choice of medication will be based on patient and family preferences. Families will be counseled on the advantages and disadvantages of these two therapies. Both medications are known to effectively suppress the hypothalamic-pituitary-gonadal axis. Known side effects include rash, and local injection site reactions (milder with Deslorelin). Lupron has the advantage of monthly administration and the disadvantage of an increase risk of local injection site abscess formation (Deslorelin may cause redness at the injection site but has not been reported to result in abscess formation). Lupron also may require more dose adjustments in the beginning of therapy. Anaphylactoid reactions are an extremely rare risk for both medications. Children will return to the NIH day hospital 3 months after starting LHRH analog therapy for evaluation of hypothalamic-pituitary-gonadal suppression. Those patients who are currently being treated with Deslorelin (previously under protocol 79-CH-112) will be continued on Deslorelin or switched to Lupron, depending on patient preference.

Once degree of CAH control has been judged optimal, children will be randomized to receive either the regimen of flutamide, testolactone or letrozole, and reduced hydrocortisone dose or conventional treatment (with hydrocortisone and fludrocortisone) until the age of 13 in the girls and 14 in the boys. At that time the regimen of flutamide, testolactone, and reduced hydrocortisone dose will be discontinued in boys so that the subjects can progress through puberty. At age 13 years, girls who are receiving flutamide and testolactone or letrozole therapy will discontinue the aromatase inhibitor therapy (to allow normal progression of puberty) and continue flutamide (to continue androgen blockade). Flutamide therapy will continue until 2 years after menarche or when final height is reached, whichever occurs first.

Children who are also receiving concurrent LHRH analog to suppress central puberty will also discontinue this agent at age 13 in the girls or age 14 in the boys. The operational definition of age 13 or 14 will be the NIH study visit that is closest to their thirteenth or fourteenth birthday. The operational definition of attainment of final height, as in our other long-term trials, will be the study visit at which the incremental growth over the previous 12 months declines to less than 1.5 cm (0.6 inch).

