If an elevation in liver function tests occurs, the following monitoring will be done. If the liver enzyme values are greater than 3 times the upper limit of normal, flutamide will be discontinued immediately. If the liver enzyme values are elevated but less than a 3-fold increase, liver function tests will be repeated immediately but the drug will not be discontinued. If the elevation is confirmed by repeat testing, the child will have weekly liver function tests for 3 weeks. If the

values are increasing by more than 10%, flutamide will be discontinued. If values are remaining the same (or within 10%), flutamide will be continued and the previous regimen of liver function test monitoring will be resumed with a minimum of monthly evaluations for the first three months. The above monitoring program was developed after consulting both the Food and Drug Administration and an internationally recognized expert on drug-induced hepatic injury. With these precautions, it is believed that the risk of serious hepatic injury, such as occurred in adults before this risk of the drug was recognized [43], can be eliminated. During the 8 years that we have used flutamide, involving approximately 30 children, no hepatotoxicity has been observed.

The use of flutamide during pregnancy may result in ambiguous genitalia in a male fetus. Other potential teratogenic effects are unknown. Ovulation and pregnancy either prior to menarche or in the first 6 months following menarche in girls with classic CAH is extremely unlikely. All female subjects have undergone genital surgery for correction of ambiguous genitalia and many require a second surgery in adolescence before sexual intercourse will be possible. These structural abnormalities further reduce the unlikely possibility of pregnancy. Patients and their parents will be counseled together and separately as to the importance of not becoming pregnant while on flutamide. We will perform a pregnancy test each visit for pubertal girls on flutamide.

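### Flutamide in girls has two conflicting stopping points: 6 months after menarche in the Précis, and 2 years after menarche or final height in the Protocol section

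*Combined protocol and SAP*

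**What the plan says.** The Précis describes treatment after age 13 in girls and ends it with a single trigger: "In girls, flutamide will be continued until 6 months after menarche".

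The Protocol section, under Study Design and Methods, describes the same transition. At age 13, "girls who are receiving flutamide and testolactone or letrozole therapy will discontinue the aromatase inhibitor therapy", while flutamide goes on. It then gives a different end: "Flutamide therapy will continue until 2 years after menarche or when final height is reached, whichever occurs first". Final height is defined there as the visit at which growth over the previous 12 months falls below 1.5 cm.

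The flutamide item in Evaluation of Benefits and Risks/Discomforts states the hazard: "The use of flutamide during pregnancy may result in ambiguous genitalia in a male fetus". It then argues: "Ovulation and pregnancy either prior to menarche or in the first 6 months following menarche in girls with classic CAH is extremely unlikely". It adds an argument from genital anatomy, "These structural abnormalities further reduce the unlikely possibility of pregnancy", and provides for counselling and a test: "We will perform a pregnancy test each visit for pubertal girls on flutamide".

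On outcomes, one of the Secondary Objectives includes "establishment of menstrual regularity in females", and the Exploratory Endpoints include the percentage of females with normal menstrual cyclicity at adult height.

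**The concern.** The two stopping rules use different intervals, and only one has a final-height trigger, so the Précis is not simply a shortened version of the Protocol section. A girl on the investigational regimen cannot be managed under both, except where they happen to coincide.

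Two things are at stake. The first is the safety rationale. The document itself states a fetal risk, and the sentence that discounts pregnancy is limited to the period up to 6 months after menarche. That window agrees with the Précis and does not address the later exposure that the Protocol section permits.

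The second is interpretation. Menstrual cyclicity is assessed at adult height. Which rule was followed can decide whether a girl is still on flutamide, recently off it, or long off it at that visit. A difference between arms in cyclicity reads differently in each case. The secondary growth measures from pubertal onset to adult height, which are to be examined by sex, span the same period. Their time windows are defined under either rule, but drug exposure within those windows may differ.

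**Working it through.** The plan states no figure for this point, so the check is a comparison of texts plus one subtraction.

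**Inputs**

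| Source | End of flutamide in girls, or period covered |
|---|---|
| Précis | 6 months after menarche; no final-height trigger |
| Protocol section | 24 months after menarche or final height, whichever is earlier |
| Flutamide risk item | Pregnancy argument covers the time before menarche and the first 6 months after it |
| Protocol section, visit schedule | NIH visits every 6 months |

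**Do both rules apply to the same girls?** The Protocol section limits continued flutamide to girls already on the investigational regimen. The Précis, read literally, gives flutamide to girls after age 13 without naming an arm. That is a further looseness, but investigational-arm girls fall under both texts.

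**Upper bound of the gap.** 24 − 6 = 18 months, and 18 / 6 = 3 visit intervals.

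**When the gap is smaller or reverses.** Let *h* be the months from menarche to final height. Let *m* be the months from menarche to the age-13 visit when menarche comes first, and 0 otherwise. The randomised regimen runs to the age-13 visit under either text.

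- With *m* = 0, the Protocol rule stops at min(24, *h*) and the Précis at 6, so the gap is min(24, *h*) − 6.
  - *h* of 24 or more: 24 − 6 = 18 months.
  - *h* = 12: 12 − 6 = 6 months.
  - *h* = 6: 6 − 6 = 0, so the rules coincide.
  - *h* = 3: 3 − 6 = −3, so the Protocol rule stops earlier than the Précis.
- With early menarche, the upper bound becomes 24 − max(6, *m*) for *m* up to 24, and 0 beyond that.
  - *m* up to 6: 24 − 6 = 18 months.
  - *m* = 12: 24 − 12 = 12 months.
  - *m* = 24: 24 − 24 = 0.

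The values of *h* and *m* are illustrations. The documents do not give the timing of menarche or final height, so only the 18-month upper bound is claimed.

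**Does the risk text cover the longer period?** The sentence on ovulation and pregnancy does not: its window ends at 6 months, which can leave up to 24 − 6 = 18 months outside it. The anatomical argument, the counselling while on flutamide and the pregnancy test at each visit carry no such limit.

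**Effect on the menstrual endpoint.** Suppose a girl reaches final height between 6 and 24 months after menarche and after her age-13 visit. The Protocol rule keeps her on flutamide up to the final-height visit. The Précis rule stops it at 6 months after menarche, or at the age-13 visit if that is later, so she is off drug when cyclicity is assessed.

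**The case against.** The strongest reply is that the Précis is a summary, possibly out of date, and that staff would follow the detailed Protocol section with its operational definitions. The study is single-site, which makes divergent practice less likely. This has some force: inconsistent practice is possible, not shown. It does not remove the conflict, because nothing in the supplied text gives the body precedence. The 6-month window also recurs in the risk item, so correcting the Précis alone could leave the risk text out of step.

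A second reply is that the safety consequence is largely handled, since counselling, pregnancy testing and the anatomical argument are not limited to 6 months. That stands. The defect is a gap in one sentence of the rationale, not an unmonitored exposure.

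A third is that the effect on endpoints is narrow. Cyclicity is one exploratory endpoint in girls, though it serves a secondary objective. Age at menarche precedes any stop timed from menarche, and polycystic ovarian syndrome, although hypothesised about in the Introduction, is not a listed endpoint. This also stands, and it limits the point to menstrual outcomes and, less directly, to exposure during pubertal growth.

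Finally, the consent pages and the SAP appendix cited under Analysis of Study are not in the supplied text. They could show what families were told or how exposure is to be reported, but they would not cure a contradiction within the protocol.

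**Conclusion.** The concern holds. The Précis and the Protocol section give incompatible stopping points for flutamide in investigational-arm girls, and the time-limited pregnancy sentence matches only the shorter one. Permitted exposure after menarche can differ by at most 18 months. The actual difference for any girl depends on when menarche and final height occur; it can be zero, or reverse.

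The contradiction itself is certain; its consequences in practice are not. The primary comparison of adult height remains defined under either rule. The conflict should still be fixed, because it concerns how long girls take a drug with a stated fetal risk and how their menstrual outcomes are to be read.

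**What to change.** Reconcile the Précis and the Protocol section so that one stopping point for flutamide in girls appears throughout, and state to which arm it applies. This review takes no position on which stopping point that should be. Then reconcile the time-limited ovulation and pregnancy sentence in the risk section with the exposure allowed under that rule, without assuming that its reassurance extends to a longer period.

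The text cannot show which rule each girl followed, so add one descriptive table by arm. For each girl who took flutamide, give the actual stop time relative to menarche and to the adult-height visit, and use the table when interpreting menstrual and pubertal-growth outcomes in girls. If the SAP appendix already provides this, a cross-reference is enough.

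The cost is wording changes in three places and one table from dosing and menarche records; girls are already asked to keep a menstrual calendar from menarche. No patients, visits or procedures are added.

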During flutamide and aromatase inhibitor treatment hydrocortisone dose will be decreased in 4 equal weekly steps to approximately 8 mg/m^2/day. During this month close contact will be maintained with the family by telephone and/or outpatient visits (for local patients), or referring physician visits (for distant patients), to check for symptoms or signs of adrenal insufficiency. If the hydrocortisone dosage of approximately 8 m^2/day produces symptoms or signs of adrenal insufficiency in any subject, the dosage will be adjusted on an individual basis to a dosage that will not cause symptoms or signs of adrenal insufficiency.

Patients will initially be placed on Testolactone 20 mg/kg/day of testolactone. The dose will then be increased at weekly intervals to 30 and then 40 mg/kg/day, which will be the maximum dose for the study (approximately equivalent to the usual maximal adult dose of 2 grams per day).

Patients placed on letrozole will receive a dose comparable to the dose used to suppress estrogens in adult women (1.5 mg per square meter of body surface area). This is the same dose of letrozole used for the treatment of girls with McCune Albright Syndrome.

Flutamide will also be administered in increasing doses. Patients will initially be placed on 5 mg/kg/day of flutamide. The dose will then be increased at weekly intervals to 7.5 and then 10 mg/kg/day, which will be the maximum dose for the study. This is approximately the same dose used to treat men with prostate cancer (750 mg/day, or about 10 mg/kg/day).

Subjects will be evaluated as outpatients, day-hospital patients, or inpatients on the pediatric endocrine ward at 6-month intervals until final adult height is attained. The following evaluations will be made:

- (1) Ten standing height measurements by stadiometer.
- (2) Ten sitting height measurements.
- (3) Weight.
- (4) Bone age.
- (5) Two 24-hour urine collections for cortisol.

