(18) Photographs will be taken with the patient wearing a bathing suit or underwear. This will be done at the beginning of the study and then yearly thereafter.

(19) If clinically indicated, an adrenal ultrasound and/or an additional MRI of the abdomen and adrenals may be done at follow-up visits.

(20) An apparent cortisol metabolic clearance rate determination will be performed in all patients. In patients in the flutamide-testolactone treatment group, this test will be performed twice, once off flutamide and testolactone and once on flutamide and testolactone.

Determining the apparent cortisol metabolic clearance rate in our CAH patients will enable us to determine if a patient's dose of hydrocortisone is related to their metabolic clearance of cortisol and if flutamide and/or testolactone interfere with the metabolic clearance of hydrocortisone. Cortisol metabolic clearance rate will be determined by infusing hydrocortisone overnight, starting at 6:00 p.m. and ending the hydrocortisone infusion at 2:00 a.m., at an infusion rate of 0.6 mg/m2/hour. Oral hydrocortisone will be withheld on the day of testing. This testing will be done at the randomization visit for all new patients. Patients already on flutamide and testolactone will have one of their visits extended by 3 days in order to perform this testing on and off flutamide and testolactone.

(21) Psychological assessment will be performed at baseline and completion of the study. The following standard tests will be performed: Wechsler Intelligence Scale to determine IQ, California Verbal Learning Test to evaluate verbal-memory skills, Woodcock Johnson Achievement Tests to identify learning disabilities, Bender-Gestalt Test to evaluate visual-motor skills and Continuous Performance Test to evaluate attention. Additional testing may be performed if clinically indicated. If desired, a report will be provided to the parents for potential use by the child's school. Patients will be invited to participate in an NIMH study involving magnetic resonance imaging of the brain to examine the effects of androgen exposure on brain morphology. The proposed psychological assessment will augment this data. We plan to collect data prior to the onset of puberty and after puberty.

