#### Hydrocortisone Dose Adjustment During Conventional Treatment

We will attempt to optimize the child's management during a baseline period. While administering hydrocortisone (preferably in a dose of 10-15 mg/m^2/day, and not exceeding 25 mg/m^2/day), the mineralocorticoid dose will be adjusted to maintain a normal plasma renin activity in children with 21-hydroxylase deficiency. With plasma renin activity in the normal range, hydrocortisone dose will generally be increased if:

(1) the growth rate is 2 standard deviation (SD) units or more above the median normal value for age;

(2) the rate of bone age advancement exceeds 2 years per chronologic year; or

(3) plasma 17-hydroxyprogesterone (17-OHP) levels are excessively elevated in association with growth rate and rate of bone maturation that are above the median normal values.

Because spot measurements of plasma 17-OHP correlate rather poorly with growth rate and bone maturation, plasma 17-OHP will be used as an aid to judgement rather than as a treatment goal in itself. At the present time, 0800-0900 plasma 17-OHP levels of 500 to 1300 ng/dL are considered appropriate, levels of 1300 to 3000 ng/dL prompt consideration of a hydrocortisone dose increase (assuming that plasma renin activity is normal), levels of 3000 to 6000 ng/dL prompt strong consideration, and levels >6000 ng/dL will ordinarily lead to a dosage increase.

Hydrocortisone dose will generally be decreased if:

(1) the growth rate is 2 SD units or more below the median normal value for age, if the bone age is prepubertal, or the growth rate seems inappropriately suppressed relative to age and bone age, if the bone age is in the pubertal age range;

(2) the body mass index exceeds 2 SD units above the median value for age, or if signs of Cushing's syndrome are appearing;

(3) there is no detectable bone maturation over a period of more than 6 months; or

(4) plasma 17-OHP appears excessively suppressed in association with a subnormal growth rate or rate of bone maturation. Plasma 17-OHP levels below 500 ng/dL will ordinarily raise consideration of a dosage decrease; levels below

200 ng/dL will raise strong consideration.

We have chosen a thrice-daily hydrocortisone dose schedule for this study. There are no controlled studies that compare a twice-daily and thrice-daily approach; however the thrice-daily hydrocortisone dose schedule is the most commonly used conventional regimen.

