#### Hydrocortisone Dose Adjustment During Investigational Treatment

Congenital adrenal hyperplasia occurs in several clinically distinct variants that reflect differing severity of the underlying enzymatic deficiency, even among the classic forms. For example, the salt-wasting and simple-virilizing forms of 21-hydroxylase deficiency have different clinical courses: salt-wasters experience many more episodes of adrenal crisis and may require more glucocorticoid for adequate control. Even within the salt-waster and simple-virilizer subgroups of CAH, clinical heterogeneity is seen. This may be due to varying genotypes or other unknown factors.

A hydrocortisone dose of 8 mg/m2/day was chosen in our initial pilot study based on estimates of normal production rate; however, children may vary in their glucocorticoid daily requirements. Our hypothesis that the regimen of flutamide, an aromatase inhibitor and a reduced hydrocortisone dose can normalize the growth of children with, CAH while avoiding the complications of supraphysiologic glucocorticoid, does not require identical glucocorticoid doses in all children on the new regimen. Regimens will be more closely tailored to the individual differences in glucocorticoid requirement. The hydrocortisone dose will be allowed to vary in the flutamide-aromatase inhibitor treatment arm.

With plasma renin activity in the normal range, hydrocortisone dose will generally be increased if 2 or more of the following occur:

- 1) the rate of bone age advancement exceeds 2 years per chronologic year and there is no evidence of central precocious puberty as the cause;
- 2) plasma 17-hydroxyprogesterone levels exceed 10,000 ng/dL;
- 3) plasma androstenedione levels exceed 400 ng/dL;
- 4) testosterone levels exceed 100 ng/dL in girls or prepubertal boys;

- 5) signs of virilization (clitoral growth, voice deepening, acne) on physical examination;
- 6) presence of adrenal rest tissue on testicular ultrasound in boys (see below);
- 7) evidence of macronodular disease on adrenal ultrasound or MRI (see below).

With plasma renin activity in the normal range, hydrocortisone dose may be decreased if 2 or more of the following occur:

- 1) plasma 17-hydroxyprogesterone levels are below 500 ng/dL;
- 2) plasma androstenedione levels are below 50 ng/dL;
- 3) the rate of bone age advancement is less than 1 year per chronologic year;
- 4) weight percentile is greater than or equal to height percentile.

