(6) Since hydrocortisone dosage will be reduced below that usually employed, some patients may develop symptoms or signs of adrenal insufficiency. We consider that this is unlikely to be a serious risk because; (1) patients will continue to receive an optimal fludrocortisone dose, (2) CAH patients remain capable of producing some endogenous hydrocortisone, and (3) the restricted dosage of approximately 8 mg/m^2/day is equivalent to the most recent estimates of normal production rate and, in concert with the first 2 factors, should prevent any subjects from experiencing adrenal crisis. If, however, symptoms or signs of adrenal insufficiency do occur at this dosage, the hydrocortisone dose will be increased on an individual basis to a dose that does not cause such signs or symptoms.

(7) Efficacy of the new treatment approach. Since the new approach to be tested in this study has only been employed previously in short-term studies, there is the theoretical possibility that its long-term effectiveness could be less than that of conventional therapy. In this event participants randomized to the investigational regimen would miss the full benefit of conventional treatment.

(8) Leuprolide stimulation test. This is a standard test of pubertal onset. It has no known risk.(9) ACTH test. This is a standard test of adrenal function. It has no known risk.

(10) Bone density of the forearm, femur, and lumbar spine will be determined annually by DEXA. (Bone age x-rays of the wrist will also be performed every six months). The maximal tissue dose is 90 mrem to skin of lower back. The total effective dose is less than 1 mrem. Effective dose is the uniform whole-body dose, which is used to relate the dose received by each organ to a single value. The effective dose is well within the RSC guidelines for children of 500 mrem.

(11) Magnetic Resonance Imaging (MRI). This procedure is without known risk and involves no radiation exposure. Approximately 1% of subjects are too claustrophobic to be studied. During the MRI scan, the patient hears rhythmic tapping sounds due to switching on and off of the gradient coils. Subjects are warned of this prior to scanning and most do not find it objectional. Ear plugs are provided. Metal objects are exclusionary criteria and patients will be carefully screened for these exclusionary criteria. There are no known adverse effects of magnetic resonance imaging

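### The cortisol clearance test withholds oral hydrocortisone on the test day but starts the infusion only at 6 p.m., so on the natural reading a child with classic CAH goes at least 18 hours without it; giving the morning dose is a cheap safety improvement.

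*Combined protocol and SAP*

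**What the plan says.** Evaluation (20) in the Protocol section calls for a cortisol metabolic clearance test in every patient, and twice (off and on drug) in the flutamide-testolactone group. New patients have it at the randomization visit. Patients already on the drugs have one visit extended by 3 days so that both tests can be done.

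The method is "infusing hydrocortisone overnight, starting at 6:00 p.m. and ending the hydrocortisone infusion at 2:00 a.m", "at an infusion rate of 0.6 mg/m2/hour". On oral dosing the item says only this: "Oral hydrocortisone will be withheld on the day of testing". It does not exempt the morning dose, say when oral dosing resumes, give sampling times, or set a rule for a child who becomes unwell during the test.

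Three other places bear on it:

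- The section on dose adjustment during conventional treatment fixes the background schedule: "We have chosen a thrice-daily hydrocortisone dose schedule for this study".
- The Protocol section allows several settings for visits: "Subjects will be evaluated as outpatients, day-hospital patients, or inpatients on the pediatric endocrine ward".
- The benefits and risks section treats adrenal insufficiency as a consequence of the reduced maintenance dose: if "symptoms or signs of adrenal insufficiency do occur at this dosage, the hydrocortisone dose will be increased on an individual basis". Its numbered list has no entry for the clearance test.

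**The concern.** These children depend on hydrocortisone replacement, and the written rule removes it for most of a day before any replacement begins. The test is done to learn about clearance, not to treat the child, so an avoidable gap needs a reason, and none is given.

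The tested group includes salt-wasters, of whom the section on dose adjustment during investigational treatment says: "salt-wasters experience many more episodes of adrenal crisis and may require more glucocorticoid for adequate control". The written response to symptoms was drafted for the long-term dose of about 8 mg/m2/day, and it acts only once symptoms have appeared. At stake is patient safety during one procedure.

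**Working it through.** The plan states no length for the gap, so there is no figure of its own to reproduce.

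**Inputs from the protocol.** Infusion from 18:00 to 02:00 at 0.6 mg/m2/h; thrice-daily oral dosing; about 8 mg/m2/day on the investigational regimen; preferably 10 to 15 and at most 25 mg/m2/day on conventional treatment.

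**Assumptions not in the documents.** Oral doses in equal thirds at about 8 a.m., 2 p.m. and 8 to 10 p.m.; half-life T of 1 to 3 h; one compartment; immediate and complete absorption.

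**Step 1: hours without hydrocortisone before the infusion.**

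- All test-day doses held, counted from midnight: 18 − 0 = 18 h.
- Counted from a last dose at 22:00 or 20:00 the evening before: 18 + 2 = 20 h, or 18 + 4 = 22 h.
- 8 a.m. dose given: 18 − 8 = 10 h.
- 2 p.m. dose also given: 18 − 14 = 4 h.
- Ordinary night, from 20:00–22:00 to 08:00: 10 to 12 h.

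**Step 2: what the infusion supplies.** 0.6 × 8 = 4.8 mg/m2. That is 4.8/8 = 60% of the investigational daily dose, and 4.8/15 = 32% to 4.8/10 = 48% of the preferred conventional dose.

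**Step 3: carry-over if the 8 a.m. dose is given.** With D one third of the daily dose, t the clock hour (02:00 counted as 26) and k = ln2/T:

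- residual from the oral dose = D × 2^(−(t−8)/T)
- infused cortisol in the body = (0.6/k) × (1 − 2^(−(t−18)/T))

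At 02:00 the infused amount is 0.862, 1.623 and 2.188 mg/m2 for T = 1, 2 and 3 h. For T = 3 h and 8 mg/m2/day, D = 8/3 = 2.67, the residual is 2.67 × 2^(−6) = 0.0417, and 0.0417/2.188 = 1.9%. At 22:00 the infused amount is 1.566 mg/m2, the residual is 2.67 × 2^(−14/3) = 0.105, and the ratio is 6.7%. In the same way:

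| Daily dose (mg/m2) | 02:00, T = 1 h | 02:00, T = 2 h | 02:00, T = 3 h | 22:00, T = 3 h |
|---|---|---|---|---|
| 8 | 0.001% | 0.32% | 1.9% | 6.7% |
| 15 | 0.002% | 0.60% | 3.6% | 12.6% |
| 25 | 0.004% | 1.0% | 6.0% | 21% |

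**Step 4: the midday dose.** A 2 p.m. dose is only 12 h old at 02:00. For T = 3 h it adds 2.67 × 2^(−4)/2.188 = 7.6% at 8 mg/m2/day and 5 × 2^(−4)/2.188 = 14.3% at 15 mg/m2/day. The calculation therefore supports giving the morning dose but not the midday one.

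**Step 5: the protocol's own safety argument on this day.** The benefits and risks section gives three reasons why adrenal insufficiency is unlikely to be serious: optimal fludrocortisone, some endogenous production, and about 8 mg/m2/day of hydrocortisone. The first two still hold on the test day. The third does not hold before 6 p.m.

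**The case against.** **The 18 hours depend on one reading.** The test runs across midnight, and the sponsor may have meant only the doses close to the infusion, which would make the gap 10 or 4 hours. The text does not say so. Evaluation (7), by contrast, says explicitly that the morning dose is only delayed until blood has been drawn. The calendar-day reading remains the natural one, and ward staff have nothing else to go on.

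**Protection remains.** Only oral hydrocortisone is withheld, not fludrocortisone. The Introduction defines salt-wasting by a lack of mineralocorticoid, which is still replaced. This stands and lowers the risk. It does not lower it to nothing, since the protocol also says that salt-wasters may need more glucocorticoid.

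**Supervision is likely.** An overnight infusion and a visit extended by 3 days suggest inpatient care, and the team would very probably treat a symptomatic child. Only presence before 6 p.m. is left unstated.

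**The 8-hour average interval is a weak yardstick.** Ordinary nights already run to 10 to 12 hours. The fair comparison is 18 to 22 hours against those.

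**Carry-over is not negligible in every case.** A reader might infer that the morning dose has virtually no effect on the measurement. The documents give neither a half-life nor sampling times, and a sample at 10 p.m. could carry 7 to 21%. The model also leaves out the oral dose's suppression of endogenous cortisol through ACTH. The dose is safe for the measurement only if sampling is late.

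**Two further inferences go too far.** One is that the test puts children in adrenal crisis: the documents give no crisis rate for such a gap. The other is that families were not told: the consent pages were not available, so only the protocol's own risk list can be judged.

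**Conclusion.** The point holds as a minor safety matter and a cheap improvement. As written, and on the natural reading, evaluation (20) leaves a child with classic CAH without hydrocortisone for at least 18 hours, or 20 to 22 hours if the last dose was at 8 to 10 p.m. Two of the protocol's three stated protections still apply; the third is absent until 6 p.m. The size of any harm cannot be estimated from the documents.

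Cortisol clearance is not among the listed endpoints, so nothing here touches the adult-height comparison or any other endpoint analysis.

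The 18 hours rest on the protocol's clock times and on taking the test day as a calendar day. The carry-over figures rest on the assumed half-life, dose times, equal thirds and absorption.

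**What to change.** Replace the sentence in evaluation (20) with:

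*On the day of testing the usual morning oral hydrocortisone dose is given by 8 a.m., after any samples for item (7). Later oral doses that day are withheld, and the usual morning dose is given after the infusion ends. If the child shows symptoms or signs of adrenal insufficiency, the test is abandoned and hydrocortisone is given at once at a treatment dose, without interrupting intravenous cover.*

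The last clause matters. The infusion runs at 0.6 × 24 = 14.4 mg/m2/day, so stopping it in favour of one oral maintenance dose (about 2.7 mg/m2 for a child on 8 mg/m2/day) could reduce cover when it is most needed.

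Also state that clearance is calculated from samples late in the infusion, and add one line for this test to the numbered risk list.

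The gap before the infusion falls from at least 18 to about 10 hours, so the longest gap becomes the ordinary overnight one of about 10 to 12 hours. The cost is a few lines of text and the carry-over shown above: at most about 2 to 4% at 2 a.m. for 8 to 15 mg/m2/day and about 6% at the 25 mg/m2/day ceiling. No extra patients are needed.
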